4.2 Exclusion criteria

- 1) Any other form of diabetes mellitus than type 2 diabetes mellitus, history of diabetic ketoacidosis
- 2) Ongoing ventricular arrhythmia
- 3) Known allergy to SGLT-2 inhibitors
- 4) Hemodynamic instability as defined by intravenous administration of catecholamine, calcium-sensitizers or phosphodiesterase inhibitors
- 5) >1 episode of severe hypoglycaemia within the last 6 months under treatment with insulin or sulfonylurea
- 6) Planned catheter ablation for ventricular arrhythmia within upcoming 12 months
- 7) Planned explantation of ICD, or planned up/downgrade to/from CRT-D device within upcoming 12 months
- 8) Existing therapy with SGLT-2 inhibitors

4.3 Withdrawal criteria

Subjects may be withdrawn from the study at the discretion of the Investigator or Sponsor due to a safety concern or if judged non-compliant with trial procedures. A subject must be withdrawn from treatment of the following applies:

- Subject chooses to withdraw from the study at any time
- Adverse event requires unblinding of the study medication

- Pregnancy or intention of becoming pregnant
- Intolerable adverse effects
- Major violation of the study protocol
- Occurrence of an exclusion criterion
- Other circumstances that would endanger the health of the subject if he/she were to continue his/her participation in the trial.

Reasons for withdrawals and discontinuation of any subject from the protocol have to be recorded.

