5.4 Visit procedures

Visit 1 - Screening/Enrolment Visit (Day 0)

- Obtain informed consent of potential participant verified by signature on study informed consent form (10.5)
- Collect blood for routine biochemistry and to check inclusion criteria (eGFR, nt-proBNP) (5.5.5)
- Collect and prepare blood samples for biobank (5.5.6)
- Obtain demographic information, medical history, medication history and tobacco use history (5.5.1)
- Perform ECG, echocardiography, ICD interrogation (5.5.2)
- Record vital signs (5.5.3)
- Measure body weight and body height (5.5.4)
- Verify inclusion/exclusion criteria (4.1 and 4.2)
- Randomize the subject (5.2)
- Dispense the study medication for trial period (9.4)
- Adjust concomitant antihyperglycaemic medication
- Assessment of side effects and patient safety before discharge

Visit 2 - Follow-up Visit (Week 52 ± 4 weeks)

- Record adverse events as reported by participant or observed by investigator (6.1 – 6.5)
- Perform echocardiography, ICD interrogation (5.5.2)
- Record vital signs (5.5.3)
- Measure body weight (5.5.4)
- Collect blood for routine biochemistry (5.5.5)
- Record changes in medication (5.5.1)
- Collect and prepare blood samples for biobank (5.5.6)
- Record participant's adherence to treatment program
- Drug accountability (9.5)

Visit 3 - Telephone assessment (4 weeks ± 1 week after V2)

- Record adverse events as reported by participant (6.1 – 6.6)

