5.5.2 ECG, echocardiography, ICD interrogation

An ECG, echocardiography, and ICD interrogation will be performed at the screening visit. In our study, ICDs are interrogated both with telemedicine (home-monitoring) and during on-site ICD follow-ups.

Patients will be offered to be included in our home-monitoring program. Currently, already 80% of patients have a home-monitoring device and routinely (every 4 months) transmit their data. In case of an alarm (sustained VT/VF) the data is transmitted automatically. In addition, all patients, regardless if they have a home-monitoring device or not, will be checked in the outpatient clinic on a yearly basis.

All arrhythmic events are recorded in the patient database. For this study, the number of episodes recorded during the study period will be tallied up.

All tests will be interpreted, signed and dated by the investigator before randomisation.

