7.2 Data analysis

Intention-to-treat (ITT) analyses will be applied as the primary analysis. Analysis of the primary endpoint is comparison of the number of sVT/VF episodes between treatment groups from randomization to week 52. The primary endpoint will be analysed using analysis of covariance (ANCOVA), with treatment as a fixed factor, the baseline number of sVT/VF episodes as a covariate and with adjustment for history of T2D and eGFR and site of randomization.

Normally distributed variables will be presented as mean \pm standard deviation (SD) and skewed distributed variables as median and interquartile range [IQR]. Comparisons between treatment and placebo group will be performed by an unpaired two sample *t*-test, Mann–Whitney test, or χ^2 test as appropriate.

A two-tailed p-value ≤ 0.05 will be considered statistically significant. A detailed statistical analysis plan including pre-specified subgroup analyses will be finalized ahead of database lock.

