9.4 Dispensing of Study Drug

The study team shall dispense the study drug only to subjects entered into the study, under the direction of the PI or sub-investigators authorized to receive or dispense it. The study drugs will not be dispensed or supplied to any person not authorized to receive it. Each time a study drug is dispensed; there must be documentation in the sponsor provided log (drug accountability log) as to the amount dispensed, to whom it is dispensed, and the date and signature or initials of the person dispensing the drug. Subjects should be advised to follow the study protocol and as appropriate to protocol return all used and unused containers to the site at study visit 2 (week 52). Any discrepancies between the amounts used by the subjects and the amount returned should be documented.

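### Protocol 4.3 allows withdrawal from the study for non-compliance, and neither document continues ICD data collection after withdrawal, so the ITT primary analysis is open to informative loss of follow-up

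*Protocol*

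**What the plan says.** Protocol 4.3 opens with a discretionary rule on when a subject may be taken out of the trial: "withdrawn from the study at the discretion of the Investigator or Sponsor due to a safety concern or if judged non-compliant with trial procedures". Non-compliance is not defined further. A mandatory list follows, introduced by "A subject must be withdrawn from treatment of the following applies". Its first entry is the subject's choice to leave the study, so ending drug and ending participation are not kept apart. The section closes with "Reasons for withdrawals and discontinuation of any subject from the protocol have to be recorded". It says nothing on what data are collected afterwards.

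The visit schedule (Protocol 5.3, repeated in SAP 3.4) has baseline, week 52 and a telephone contact, with no early-termination or post-withdrawal visit. The instruction "Record participant's adherence to treatment program" belongs to visit 2 (Protocol 5.4), as do drug accountability and the second ICD interrogation.

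Protocol 5.5.2 says that about 80% of patients have home monitoring and transmit every 4 months, that sustained VT/VF alarms are sent automatically, and that all patients are checked yearly in clinic. It adds "All arrhythmic events are recorded in the patient database".

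On analysis, Protocol 7.2 states "Intention-to-treat (ITT) analyses will be applied as the primary analysis". Neither document defines the ITT set. SAP 5 uses a negative binomial model with time at risk as the offset. SAP 5.2 plans multiple imputation if the sample size allows.

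**The concern.** An ITT comparison needs outcome data on every randomised patient for the planned period, whether or not drug was taken. A rule that lets a site or the sponsor close a patient's participation for non-compliance works against that, unless the plan also says that data collection goes on. It does not.

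The loss is unlikely to be random. Non-compliance can follow from tolerability, which may differ by arm: Protocol 5.6 names genital infection as the drug's most common side effect. It can also follow from worsening illness, which goes with more arrhythmia. In addition, occurrence of an exclusion criterion is a mandatory ground in 4.3, and the exclusion criteria include ongoing ventricular arrhythmia and planned ablation. An endpoint event can therefore itself start a withdrawal, and with treatment and study withdrawal mixed, the patient's later episodes may never be collected.

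The site also need not be blind to the events. Alarms arrive during the year, and nothing requires the compliance judgement to be made before they are seen.

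At stake are the direction and size of the primary rate ratio. The offset corrects for shorter observation, not for which patients have it. The SAP does not say whether a partial count is kept with its shorter exposure or treated as missing. Imputation from observed data cannot be relied on to repair withdrawal that depends on events not collected.

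**Working it through.** **1. What the plan allows for.** SAP 4 takes 191 per group and about 5% dropout: 2 × 191/0.95 = 402.1, the stated 402. This protects power against a loss of that size. It does nothing about bias from who is lost.

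**2. Where the gap lies.**

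| Question | Answer in the documents |
|---|---|
| Can a patient be taken out of the study for non-compliance? | Yes, at discretion (Protocol 4.3) |
| Is stopping drug kept apart from stopping follow-up? | No (Protocol 4.3) |
| Are ICD counts collected to week 52 after withdrawal? | Not stated |
| Are withdrawn patients excluded from ITT? | Not stated |
| Must the decision be blind to device events? | Not stated |

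For a withdrawal at visit 2, the week-52 count has been or can be obtained at that visit. For a withdrawal before visit 2, no text secures the remaining count. The exposure is therefore mainly to earlier withdrawals.

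**3. Illustration of size.** From the documents: control rate r₀ = 1.3 per year (SAP 4), dispersion k = 1, follow-up T = 0.95 years (11.4 months), target rate ratio 0.70. Assumed, because the documents give no figures: a share f of the ertugliflozin arm leaves at mid-period (0.475 years) with twice the arm's average rate, and placebo removals are unrelated to rate. The patients who stay then have relative rate (1 − 2f)/(1 − f), so that the whole arm averages 1.

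In a negative binomial model with an offset, the fitted arm rate is close to Σwy/Σwt, where w = 1/(1 + k·r·t) and r is the arm's rate. The bias factor in the ertugliflozin arm is

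B = [A(1 − 2f)/(1 − f) + 2H]/(A + H), with A = (1 − f)·w(0.95)·0.95 and H = f·w(0.475)·0.475.

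*True ratio 1 (r = 1.3):* w(0.95) = 1/2.235 = 0.447; w(0.475) = 1/1.6175 = 0.618.
- f = 0.05: A = 0.4038, H = 0.0147; B = (0.3826 + 0.0294)/0.4185 = 0.984.
- f = 0.15: A = 0.3613, H = 0.0441; B = (0.2975 + 0.0881)/0.4054 = 0.951.

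*True ratio 0.70 (r = 0.91):* w(0.95) = 1/1.8645 = 0.536; w(0.475) = 1/1.43225 = 0.698.
- f = 0.05: A = 0.4841, H = 0.0166; B = 0.982; 0.70 × 0.982 = 0.69.
- f = 0.15: A = 0.4331, H = 0.0497; B = 0.945; 0.70 × 0.945 = 0.66.

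The Protocol's control rate of 1.0 gives the same values to two decimals. Fitting the model to simulated counts agrees within simulation error.

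A crude ratio of events to time overstates the shift. At f = 0.15 it gives (1 − 0.15)/(1 − 0.075) = 0.92, and 0.70 × 0.919 = 0.64. The planned model moves less because patients with shorter follow-up keep more weight per unit of time.

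The direction rests on the assumption. If the higher-rate leavers were in the placebo arm instead, a true ratio of 1 would read about 1/0.951 = 1.05 at f = 0.15.

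**The case against.** The strongest reply is that 4.3 governs participation, not the analysis set. No text excludes withdrawn patients or discards their data. ITT is stated, unequal follow-up has an offset, imputation is planned, and the yearly device check applies to all patients. Most of this stands, and it limits the point in four ways.

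- **A contradiction with ITT.** A reader might infer that 4.3 contradicts 7.2, or turns the trial into a comparison of compliers. The documents do not support that. Conflict arises only if device follow-up stops or counts are dropped. What is missing is the text that would prevent this.
- **Removal at visit 2 with the count in hand.** A reader might infer this because adherence and ICD interrogation fall at the same visit. But withdrawal then formally ends only the telephone contact, and nothing permits deleting a count. Also, 4.3 speaks of compliance with trial procedures, not specifically with drug.
- **Inflated type I error.** Patients and physicians are blinded (Protocol 3.1). In simulations with 201 per arm, discarding the top 5% of pooled counts without regard to arm gave 4.0% two-sided rejection under no effect. With a true 0.70 it moved the ratio to 0.79 and power from 71% to 40%. Discarding the top 5% in the active arm only gave 0.79 and 44% rejection under no effect. These figures assume discarding that no text provides for. Blinding limits deliberate selection by arm, but not loss driven by tolerability.
- **Size.** At the planned dropout of about 5%, the shift is about 2% even with selection in one arm only. The 15% case is three times the plan's allowance.

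Timing is a fair practical objection too. SAP section 7 reports early termination, and that version is dated 19/02/2024, after the last visit planned in the Protocol synopsis (January 2024). New protocol wording may come too late to extend follow-up. Rules for the analysis set and for retrieving stored device data would not.

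**Conclusion.** The point holds as an unprotected ITT analysis, not as a contradiction. Protocol 4.3 gives an undefined, discretionary route out of the study for non-compliance and mixes it with stopping drug. No text secures ICD data to week 52 afterwards. The offset and conditional imputation do not repair a loss that depends on arm and arrhythmia rate. The main exposure is withdrawal before visit 2, when alarms may already have shown the site some of the events.

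The likely size is modest. With leavers at twice the average rate in the ertugliflozin arm only, a true ratio of 1 reads about 0.98 (5% leaving) to 0.95 (15%), and a true 0.70 reads about 0.69 to 0.66. The share, timing, relative rate and one-sidedness are all assumptions, and the shift could go the other way. The change is worth making because the data are largely there to be had and the remedy is cheap.

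**What to change.** **Protocol 4.3.** Remove non-compliance as a ground for ending data collection. Separate end of treatment from end of data collection, and leave the grounds for stopping study drug, including safety, as they are. State that every randomised patient stays in follow-up unless consent for data is withdrawn. State that sVT/VF, nsVT, ICD therapies, hospitalisations and vital status are then taken from home monitoring, the yearly device check and the telephone visit.

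**SAP.** Define ITT as all randomised patients. Retain every count obtained, with its time at risk. Retrieve device data to week 52 where consent allows. Report withdrawals by arm, reason and date. If follow-up has already closed, this is the part that can still be carried out, and it should be settled before the analysis.

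**Cost.** Protocol and SAP wording, and longer follow-up of some patients by the sites. Off-drug time enters the estimate, which is what an ITT analysis intends. The stated sample size does not change.

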Time schedule	
With reference to the trial:
 
EC Submission: NOV/2020
 
Local Authority Submission: SEP/2020
 
First Patient First Visit (FPFV): JUN/2021

Last Patient First Visit (LPFV): JAN/2023

Last Patient Last Visit (LPLV): JAN/2024

Data Base Lock: APR/2024

First Results available: JUN/2024

Clinical Study Report: JUN/2024

With reference to patients:

Duration of the treatment: 12 months

Main inclusion criteria

- 1) HFrEF or HFmrEF, and ICD±CRT therapy > 3 months
- 2) At least 10 documented VT episodes (either nsVT or sVT ± ICD treatment) within the last 12 months plus:
 - nt-proBNP > 500pg/mL or
 - LV-EF < 35% or
 - hospitalization for heart failure within the last 12 months or
 - >100nsVTs within the last 12 months
 - >1 sVT/VF within the last 12 months
- 3) Informed consent has to be given in written form.
- 4) eGFR > 30 ml/min/1.73m²
- 5) Blood pressure before first drug dosing: RR_{systolic} >100mmHg
- 6) Blood pressure before first drug dosing: RR_{diastolic} >60mmHg
- 7) 18 – 80 years of age

Main exclusion criteria

- 1) Any other form of diabetes mellitus than type 2 diabetes mellitus, history of diabetic ketoacidosis
- 2) Ongoing ventricular arrhythmia
- 3) Known allergy to SGLT-2 inhibitors
- 4) Haemodynamic instability as defined by intravenous administration of catecholamine, calciumsensitizers or phosphodiesterase inhibitors
- 5) >1 episode of severe hypoglycaemia within the last 6 months under treatment with insulin or sulfonylurea
- 6) Planned catheter ablation for ventricular arrhythmia
- 7) Planned explantation of ICD, or planned up/downgrade to/from CRT-D device

Study medication

Active substance: Ertugliflozin

Commercial name: Steglatro

Manufacturer: MSD

Treatment plan

Ertugliflozin, 5mg once daily orally administered or matched placebo

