5. VISIT PROCEDURES, MEASUREMENTS AND ASSESSMENTS

5.1 Recruitment and screening

Sites will recruit competitively and sites will receive compensation for their work based on a per-patient fee. The clinic staff of the EP/arrhythmia service informs patients about the possibility of being enrolled in this study. No study-related procedures are undertaken before obtaining informed consent. The study team in detail explains the study procedures and asks the participant about their willingness to participate in this research study. After informed consent is signed and obtained, participants are given a signed copy of the informed consent document and are assigned a screening identification number.

After obtaining informed consent at the screening visit, subject's eligibility will be further assessed and documented by using a source data form with a list of inclusion and exclusion criteria, medical history (including all medications past and current) will be acquired and the following measurements will be performed: body weight, height, blood pressure, ECG and blood parameters (see Table 2). Laboratory results up to 14 days before screening can be used to test eligibility for the trial.

Subjects unable to provide written informed consent will not be included in the study.

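### Protocol 4.3 makes pregnancy a mandatory stop, but visit 1 randomises and dispenses 52 weeks of drug with no pregnancy exclusion and no listed pregnancy test

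*Protocol*

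**What the plan says.** Protocol 4.3 lists the conditions under which treatment must stop. One of them is "Pregnancy or intention of becoming pregnant".

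Protocol 5.4 sets out visit 1 as a list of 12 steps. Step 2 is a blood draw: "Collect blood for routine biochemistry and to check inclusion criteria (eGFR, nt-proBNP) (5.5.5". Step 8 is the eligibility check: "Verify inclusion/exclusion criteria (4.1 and 4.2". Step 9 is randomisation, and step 10 is "Dispense the study medication for trial period (9.4". Section 9.1 says that the pharmacy packs the medication as 52-week supplies. The next on-site study visit is at week 52 ± 4.

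Section 4.1 admits ages 18 to 80, with no condition on sex, contraception or childbearing potential. Section 4.2 has 8 exclusions, the last being "Existing therapy with SGLT-2 inhibitors"; none concerns pregnancy. Section 5.1 adds a general laboratory allowance: "Laboratory results up to 14 days before screening can be used to test eligibility for the trial".

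**The concern.** The sponsor has already decided that a pregnant patient must not continue on this drug, so no outside pharmacology is needed to make the point. The entry procedure simply does not apply that decision.

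Visit 1 is the only study visit before the first dose. It is therefore the one planned opportunity to find an existing pregnancy before exposure. If it is missed there, the patient goes home with a year of tablets, and no on-site study visit is scheduled until about week 52. The device follow-up in between (5.5.2) is not directed at pregnancy.

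There are two gaps, of different weight:

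- **No baseline test is listed.** This is the main gap, because an early pregnancy that the patient does not know about cannot be found by asking.
- **4.2 does not match 4.3.** A known pregnancy, or a stated intention, is a reason to stop but not a reason to exclude. This is smaller, because an investigator who knows 4.3 would probably act on it.

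**Working it through.** No arithmetic applies beyond counting. The check is whether any written step before the first dose would identify a pregnancy.

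**Where pregnancy could have been named**

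| Place | Items | Items on pregnancy |
|---|---|---|
| Protocol 4.1, inclusion | 7 | 0 |
| Protocol 4.2, exclusion | 8 | 0 |
| Protocol synopsis, exclusion | 7 | 0 |
| Protocol 5.4, visit 1 steps | 12 | 0 |
| Protocol Table 1, visit schedule | 21 | 0 |
| Protocol Table 2, blood tests | 21 | 0 |
| SAP 3.2.2, exclusion | 7 | 0 |
| SAP 3.4, visit table | 22 | 0 |

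The synopsis exclusions end with "Planned explantation of ICD, or planned up/downgrade to/from CRT-D device", and SAP 3.2.2 ends with the same criterion. In the protocol text supplied, pregnancy is named in two places only: 4.3, as a withdrawal reason, and 11.1, where pregnancy forms are listed among the source data. Neither is an entry step.

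**Following a patient with an unrecognised pregnancy through visit 1**

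1. Step 2, blood draw: the eligibility tests named are eGFR and nt-proBNP. Table 2 has no pregnancy test.
2. Step 4, history: it covers demographics, illnesses, medication and tobacco. A history could bring out a known pregnancy but not an unrecognised one.
3. Physical examination (Table 1 and 5.5.1): its stated focus is heart, lungs and abdomen.
4. Step 8, eligibility: the reference is to 4.1 and 4.2. The patient meets both.
5. Steps 9 and 10: the patient is randomised and receives the full supply.
6. Step 12, safety assessment before discharge: it is generic, does not name pregnancy, and comes after dispensing.

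The patient passes every written step.

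**Whether 4.3 closes the gap by itself.** It does not. Step 8 does not refer to 4.3. The 4.3 item on the occurrence of an exclusion criterion cannot help either, since pregnancy is not an exclusion criterion.

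**Comparison within 4.2.** Exclusions 6 and 7 already screen out plans for the coming 12 months (ablation, device removal, device change). Screening out a foreseeable mandatory stop follows the same logic.

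**The case against.** The omission itself is not in dispute. The arguments against giving it weight are these.

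- **A rule to stop when pregnancy is known does not by itself require a test at entry.** This is fair as a matter of logic, and the documents give no reproductive-risk data for the drug. But the rule's purpose is to keep pregnant patients off treatment, and an unrecognised pregnancy at baseline can be found only by testing.
- **Investigators would catch it.** They probably would for a known pregnancy or intention, given the mandatory wording of 4.3 and its catch-all on endangering health. This reduces the 4.2/4.3 mismatch to a minor inconsistency. It does not reach the unrecognised case.
- **Other documents may cover it.** Section 11.1 shows that some pregnancy process exists, and 11.6 refers to procedure manuals given to investigators. Those documents and the consent pages could not be read. This limit stands: the finding is about the protocol body and the SAP. Consent wording would still not be an eligibility criterion or a scheduled test.
- **It is rare, and one baseline test leaves the following year uncovered.** Both statements are true. Pregnancies that begin after visit 1 remain governed by 4.3 and are outside this point.
- **The trial stopped early** (SAP section 7). This limits the practical benefit to any enrolment still made under this protocol. The text is unaffected.

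**Conclusion.** The concern holds. Followed as written, the entry procedure can randomise and dose a patient whom 4.3 says must come off the drug. The only remaining visit 1 check is generic and comes too late.

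The number affected is likely to be small. Women of childbearing potential should be a small minority of a heart-failure population with implanted devices, and those with an undetected pregnancy on the day of visit 1 a fraction of that minority. This is an assumption; the documents give no figure. The effect on sample size, power and the primary result is negligible.

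This is a patient-safety gap that should be closed. It ranks below any issue that bears on the trial's conclusions. Confidence is high that no check is listed in the protocol body or the SAP. Whether sites carry one out under other instructions is unknown.

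**What to change.** 1. **Add a test.** In the visit 1 list of Protocol 5.4, before step 9, and in Table 1, add a pregnancy test in women of childbearing potential, with the result available before randomisation and dispensing. Use a urine test, or serum from the step 2 draw if the local laboratory reports it within the same visit. State that the 14-day laboratory allowance in 5.1 does not apply to this test, because an older negative result could miss an early pregnancy.
2. **Align 4.2 with 4.3.** Add pregnancy, or the intention of becoming pregnant, as an exclusion, so that step 8 checks it.
3. **Carry it through.** Mirror the exclusion in the synopsis and SAP 3.2.2, and the test in the SAP 3.4 visit table, so that the documents agree.

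The cost is one exclusion line, one visit item, and a routine test with a short wait in a few women. Serum depends on same-visit reporting, which a urine test avoids. The change needs Ethics Committee approval as an amendment (10.3.2). Sample size and analysis are unchanged.
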